7.3. Data Analysis Plans

We will calculate the inter-subject and intra-subject variability and estimate the ICC and its confidence interval for both the T1 and T2 values of normal breast tissue between the two MRF sequences at pre-contrast phase, and the post contrast delayed phase, respectively, to establish the parameter stability between scan times. We will also estimate the T1, T2 value change from pre to post contrast enhancement phases to establish the baseline value of normal breast parenchyma at pre and post contrast enhancement phases. We will compare the results with previous literature [19] and use independent two sample t-test to check if significant difference between MRF and with results in previous literature does not exist.

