5. INVESTIGATIONAL DEVICE

5.1. Investigational Device Description

Investigational sequences will be developed at UNC. The proposed study will be performed on the 1.5T MR scanners: (1) Main campus Siemens Avanto, Invivo 7-channel; (2) Out-patient Imaging center: Siemens Magnetom Aera, Sentinel Coil. The scanners are FDA approved and all new sequenced

possess the same safeguards as standard (FDA approved) clinical sequences to prevent harm to subjects. The study does not need any contrast administration unless it is required for standard clinical examination. For each consented subject, the additional scans will add no more than 12 minutes to the total scanning time. That is 6 minutes with two MRF sequences (3 minutes on each MRF sequence) pre-contrast enhancement phase and 6 minutes with two MRF sequences at the end of post contrast enhancement phase.

The investigational MR protocol will be implemented on the existing MR scanners without any modifications to the existing, FDA approved machine, equipment, or safety standards. Patients will receive their standard of care imaging. In addition, they will receive the research sequence. The additional sequences will be performed at no cost to the patient other than a small increase in the amount of time spent inside the MR scanner. The additional sequences are no more than 12 minutes and do not place individuals at any increased risk.

The research images will not be interpreted or analyzed for clinical decisions related to the patient. As such, this study will request that the IRB make a determination that this study is no greater than minimal risk. This study meets all the requirements for an NSR determination including:

- The device will not be implanted.
- The device is not intended to support or sustain human life.
- The device is not being used of substantial importance in diagnosing, curing, mitigating, or treating disease.
- The device does not present a potential for serious risk to health, safety, or welfare of a subject.

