7.2. Sample Size and Accrual

Our objective is to approximate the reliability for the 3D MR Fingerprinting method, which can be quantified by the Intraclass Correlation Coefficients (ICC). Given the previous preliminary experience of [name] using 3T MRI in Case Western Hospital, the ICC for T1 and T2 MRF are 0.82 and 0.875, respectively, with 12 healthy pre-menopausal volunteers scanned twice within 7-15 days. Suppose we choose 30 normal subjects and select 2 breast tissue locations for both left and right breasts for each subject to obtain 120 breast tissue images. For each breast tissue image we have two measurements using the MRF. For T1, our hypothesis test is **$H_0: ICC = 0.82$ vs. $H_1: ICC < 0.82$** , and the power will be 0.858 with significance level $\alpha = 0.05$ according to [17, 18], if the true

ICC=0.72; the power will be 0.935 with significance level $\alpha = 0.05$, if the true ICC=0.70. For T2 image, if we test $H_0: ICC = 0.875$ vs. $H_1: ICC < 0.875$, the power will be 0.969 with significance level $\alpha = 0.05$, if the true ICC=0.775; the power will be 0.873 with significance level $\alpha = 0.05$, if the true ICC=0.80; the power will be 0.749 with significance level $\alpha = 0.05$, if the true ICC=0.815. Therefore, we propose 30 normal control subjects with measurements twice, to measure the reliability of the 3D MRF technology. The measurement will be evaluated for both before and after contrast enhancement.

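### The post-contrast ICC can count real contrast-driven change between the two MRF runs as measurement error, because the ICC form is unstated and no run effect is planned

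*Combined protocol and SAP*

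**What the plan says.** Section 5.1 schedules two 3-minute MRF sequences before contrast and a further "6 minutes with two MRF sequences at the end of post contrast enhancement phase". The primary endpoint (2.2) includes the comparison of the two sequences within each phase.

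Section 7.3 estimates the ICC and its confidence interval for T1 and T2 "between the two MRF sequences at pre-contrast phase, and the post contrast delayed phase, respectively, to establish the parameter stability between scan times". It separately estimates the change in T1 and T2 from before to after contrast, so the plan itself allows for contrast altering the quantity being measured.

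Section 7.2 takes its benchmarks from earlier 3T work: "the ICC for T1 and T2 MRF are 0.82 and 0.875, respectively, with 12 healthy pre-menopausal volunteers scanned twice within 7-15 days". It powers a lower-tail test of the ICC against each benchmark with 120 tissue images and two measurements per image, and adds: "The measurement will be evaluated for both before and after contrast enhancement". No separate post-contrast benchmark is given.

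Neither section states the form of the ICC (one-way, absolute agreement or consistency), a run or time term, or a way to separate a real post-contrast change from measurement error.

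**The concern.** A test-retest ICC measures scanner reliability only if the true value is the same at both measurements. That is reasonable for two consecutive runs before contrast. After contrast, tissue concentration can change with time; section 1.2 describes converting an enhancement curve into a concentration curve. The second post-contrast run may therefore measure a slightly different T1 or T2 from the first.

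If the chosen ICC treats run-to-run differences as error, a low post-contrast value has two possible explanations, noise or contrast kinetics, and the planned analysis cannot tell them apart. A test against 0.82 or 0.875 in that phase could then reject more often than 5% even when the sequence meets the benchmark. The pre- and post-contrast ICCs would also not measure the same thing.

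**Working it through.** **Inputs from section 7.2.** Benchmarks ρ0 = 0.82 (T1) and 0.875 (T2); N = 30 × 2 breasts × 2 locations = 120; k = 2 measurements; one-sided lower-tail test; α = 0.05.

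**Step 1: reproduce the stated powers.** Let C(ρ) = (1+ρ)/(1−ρ). Reject if MSB/MSW < C(ρ0) × F0.05, so power = P[F < C(ρ0) × F0.05 / C(ρ1)]. Error df is 120 for a one-way ICC and 119 for a two-way consistency ICC. For T1 at 0.72 with 120 df: C(0.82) = 10.11, C(0.72) = 6.14, F0.05 = 0.739, and P[F(119,120) < 10.11 × 0.739 / 6.14] = 0.857.

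| Test | Stated | One-way | Two-way consistency |
|---|---|---|---|
| T1, 0.82 vs 0.72 | 0.858 | 0.857 | 0.856 |
| T1, 0.82 vs 0.70 | 0.935 | 0.934 | 0.933 |
| T2, 0.875 vs 0.775 | 0.969 | 0.968 | 0.967 |
| T2, 0.875 vs 0.80 | 0.873 | 0.872 | 0.871 |
| T2, 0.875 vs 0.815 | 0.749 | 0.748 | 0.746 |

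Both forms agree with every stated figure to within 0.003. The powers reproduce, but they do not show which ICC is meant.

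**Step 2: effect of a uniform drift on a one-way ICC.** Set the variance of a single measurement to 1 and let run 2 differ from run 1 by d in every unit. Then E(MSB) = 1 + ICC is unchanged, and E(MSW) = (1 − ICC) + d²/2. The one-way ICC becomes (2·ICC − d²/2)/(2 + d²/2). At d = 0.5 this is (1.64 − 0.125)/2.125 = 0.71 for T1 and (1.75 − 0.125)/2.125 = 0.76 for T2. An absolute-agreement ICC falls slightly less, to 0.73 and 0.78.

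**Step 3: rejection rate.** This was simulated with 120 independent units and true reliability exactly at the benchmark. All values of d are assumptions, because the documents give none.

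| Drift d (total SD) | T1 one-way ICC | T1 rejects | T2 one-way ICC | T2 rejects |
|---|---|---|---|---|
| 0 | 0.82 | 5% | 0.875 | 5% |
| 0.1 | 0.82 | 7% | 0.87 | 7% |
| 0.2 | 0.80 | 14% | 0.86 | 20% |
| 0.3 | 0.78 | 33% | 0.83 | 51% |
| 0.5 | 0.71 | 90% | 0.76 | 99% |

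With run order fitted (consistency ICC), rejection stays at about 5% at every uniform drift.

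**Step 4: drift that varies between units.** A run effect removes only the average drift. If drift also varies between units with SD 0.15 around a mean of 0.3, T1 rejection with the run effect is about 9%. With a between-unit SD of 0.25 it is about 22% for T1 and 33% for T2.

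**Step 5: reliability above the benchmark.** If same-session reliability were 0.88 for T1 (assumed), one-way rejection at 0.2/0.3 SD is at most about 0.1%/1%. At 0.92 for T2 (assumed) it is about 0.1%/3%. A drift of 0.5 SD would still matter: at an assumed T1 reliability of 0.90, about 25% of tests reject.

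**The case against.** The strongest reply is that the harm depends on three things the documents do not establish.

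- **ICC form.** A consistency ICC is unaffected by uniform drift. A reader might infer from the power figures that the plan uses a one-way ICC; Step 1 shows that they fit both forms. This part of the reply stands.
- **Drift size.** The MRF runs come at the end of the examination, after three 100-second post-contrast phases and a high-resolution scan (1.2, 5.1), so they are not on early enhancement. Drift over a few minutes could be small, and the largest figures need 0.5 total SD, about 1.2 times the T1 error SD at the benchmark (0.5/√0.18 = 0.5/0.42). This also stands: bias is possible, not shown.
- **Benchmark.** It comes from rescans 7-15 days apart, while these runs share a session. Higher same-session reliability would absorb moderate drift. Contrast might also widen between-unit variance and raise the ICC. Both are fair, but neither makes the post-contrast ICC a clean measure of scanner error.

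A reader might also infer that the plan would declare a sound sequence unreliable. The documents do not say so. Section 7.3 plans estimation with a confidence interval, the test appears only in the sample-size section, and no decision rule follows from rejection. This is a feasibility study whose research images are not used for clinical decisions.

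Finally, stability between scan times could be read as deliberately including change over time. In that case drift is worth reporting in its own right, which supports separating it from noise.

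**Conclusion.** The point holds conditionally. The plan applies the same two-run ICC in both phases, has one benchmark per parameter, leaves the ICC form open, and offers no means of separating post-contrast change from measurement error. Under a one-way or absolute-agreement form, drift can lower the post-contrast ICC. Under any form, drift that differs between units can do so.

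The size ranges from negligible (7% rejection at 0.1 SD) to severe (90% for T1 and 99% for T2 at 0.5 SD). Those figures rest on an assumed uniform drift, a one-way ICC, true reliability exactly at the benchmark, and the plan's 120 units treated as independent. They show sensitivity and are not a forecast. Only the post-contrast result is exposed; the pre-contrast ICC is not affected. The change is worth making because it costs little and makes the post-contrast result interpretable.

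**What to change.** In section 7.3:

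1. State the ICC form.
2. For the post-contrast pair, fit run order as a fixed effect and report the mean run-2 minus run-1 difference in T1 and T2 with its confidence interval.
3. Keep the test against 0.82 and 0.875 for the pre-contrast pair only, and align the closing sentence of 7.2 with this.
4. Report the post-contrast ICC with its interval as descriptive. Note that the run effect removes only the average drift, not drift that varies between locations or patients.
5. Fit the same model before contrast as a check; the mean run difference there should be near zero.

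The cost is one degree of freedom per model and the loss of a formal post-contrast benchmark test. No extra scans or patients are needed.

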1.2. Disease Background

In clinical setting, breast DCE MRI was performed for breast cancer staging, high risk screening, and problem solving when mammography, ultrasound and clinical findings were questionable. The protocol for screening MRI and clinical breast DCE MRI were the same. Patients were put on prone position with bilateral breasts fit in the dedicated breast coil. The following sequences will be taken: whole breast axial T1 weighted 3D SPGR, axial T2 weighted FSE with fat saturation, followed with axial 3D T1-weighted fat-saturated DCE MRI with one pre-contrast and three post contrast enhanced phases at the temporal resolution of 100 seconds followed with a high spatial resolution interview scan (0.9 mm isotropic 3D T1-weighted fat-saturated scan). DCE MRI has high sensitivity for breast cancer detection (95%) while lack of specificity (37-86%) between tumor types as overlap between findings of benign and malignant lesions and among different breast cancer subtypes [1]. Specifically, DCE MRI is also a powerful tool for neoangiogenesis evaluation or treatment response monitoring for breast cancer [2], with physio- pathologic measurements of the volume transfer constant (K^{trans}), fraction of extracellular extravascular space (v_e), and vascular density (v_p) [3]. To obtain these pharmacokinetic parameters, a relation between the signal enhancement and contrast agent concentrations is required. The native T1 (T_{10}) is calculated and then used to convert the signal enhancement curve to concentration curve [3]. The most commonly used method to measure T1 is variable flip angle (VFA) imaging which uses several short-repetition-time radiofrequency spoiled gradient-echo acquisitions with varying FAs [4-7]. However, the T1 measurement using VFA has been notified to be marked deviated up to 50% by the nonuniformity of the transmit radiofrequency (B_1) field even in 1.5 T [8]. It would be very important to obtain the most accurate T_{10} value of breast tumor before contrast medium injection to calculate the most accurate pharmacokinetic parameters across different platform, vendors and machines. Nevertheless, it is a daunting task to obtain quantitative measures of T_{10} independent of these potential confounding factors. The current paradigm of MRI is to use a set of scanner settings to generate an image ‘weighted’ a specific MR contrast mechanism (physical

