1.3. Conventional Imaging Modality

The clinical DCE MRI of breast have been widely used for breast cancer screening, detection, staging and treatment response monitoring for decades. This image modality outperforms mammography and ultrasound of breast in breast cancer detection and extent evaluation [11]. There is no radiation risk for this imaging examination. The only two drawbacks of this study are longer examination time and gadolinium based contrast medium usage. The patients need to be rested on the examination table in a fixed prone position (not very comfortable) with bilateral breasts been fitted in the breast coiled for at least 30 to 40 minutes.

As part of the MRI procedure subjects may receive a contrast agent called gadolinium. Gadolinium makes it easier to see details on the MRI pictures. An extremely rare disease called Nephrogenic Systemic Fibrosis (NSF) is associated with the use of gadolinium contrast agents in patients with chronic severe renal insufficiency or renal dysfunction due to hepato-renal syndrome or in the peri-operative liver transplantation period. Exclusion criteria for this study are in compliance with the Food and Drug Administration's advisory statements. If subjects have any problems with their kidneys, they may be at risk for a condition called Nephrogenic Systemic Fibrosis (NSF) or Nephrogenic Fibrosing Dermopathy. NSF has been reported to occur between 2 days and 18 months following injection of gadolinium. There is no known treatment for NSF. Some people have even died from this. Signs and symptoms of NSF may include: burning, swelling, hardening or tightening of the skin, blood vessels and internal organs (heart, lungs, liver; yellow spots on the white part of the eyes; joint swelling and stiffness; pain in the hip bones or ribs; muscle weakness.

Subjects' study doctor will check how well their kidneys work before they are given gadolinium. Depending on how well their kidneys work, they may be given a reduced dose or they may not be able to take gadolinium at all. NSF has not been reported in people with normal kidneys.

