2. STUDY OBJECTIVES

2.1. Primary Objectives

The purpose of this study is to evaluate the novel quantitative MRI techniques, namely MR Fingerprinting (MRF), in clinical studies to establish the T1 and T2 value baselines of normal glandular tissue.

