2.2. Primary Endpoint

The normal breast tissue T1, T2 value will be used to compare between sides in same patient and among the different patients and between two MRF sequences in pre-contrast phase and post contrast enhancement phase and also the differences between pre and post contrast enhancement phases.

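### The pre-to-post contrast change is planned only in raw T1 and T2, which makes it a weak basis for comparing women; a relaxation-rate change, reported with dose and delay, should stand beside it

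*Combined protocol and SAP*

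**What the plan says.** The primary objective (section 2.1) is to "establish the T1 and T2 value baselines of normal glandular tissue". The primary endpoint (section 2.2) compares T1 and T2 between sides, among patients and between repeat MRF scans, and then adds "also the differences between pre and post contrast enhancement phases".

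For that last item, section 7.3 will "estimate the T1, T2 value change from pre to post contrast enhancement phases to establish the baseline value of normal breast parenchyma". In full, the stated purpose is "to establish the baseline value of normal breast parenchyma at pre and post contrast enhancement phases". No relaxation-rate, ratio or log scale is named, and no covariate.

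On the conditions of the post-contrast measurement:

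- Section 5.1 places "6 minutes with two MRF sequences at the end of post contrast enhancement phase". No interval from injection is given.
- Section 5.1 also leaves contrast to the needs of the clinical examination, so this protocol sets neither agent nor dose.
- Section 1.3 says that, depending on kidney function, patients "they may be given a reduced dose or they may not be able to take gadolinium at all".
- Neither the medical record abstraction in section 4.2.4 nor the table in section 4.3 lists agent, dose or injection time as items to collect.

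In the background, section 1.2 says of conventional dynamic imaging: "The native T1 (T_{10}) is calculated and then used to convert the signal enhancement curve to concentration curve".

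**The concern.** A contrast agent is usually modelled as adding to the relaxation rate (1/T1 or 1/T2) in proportion to its concentration in tissue. A difference in relaxation time then mixes two things: how much agent arrived, and how long the native T1 was. Two women with the same uptake but different native T1 would show different changes in milliseconds. If the change is compared between women, or between one woman's breasts, part of what is seen may only repeat the pre-contrast difference.

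There is a separate matter of labelling. A post-contrast T1 depends on agent, dose and time since injection. Called a baseline of normal parenchyma without those facts, it cannot readily be used by another site or set beside another series.

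**Working it through.** **The plan's own figures.** No design figure is stated for the pre-to-post change. The only ones are the powers of the ICC test in section 7.2, and they reproduce. With n = 120 units, k = 2 measurements and one-sided alpha 0.05, power = Φ(√[(n−1)(k−1)/(2k)] × |ln C| − 1.645), where C = [1 + kρ0/(1−ρ0)] / [1 + kρ1/(1−ρ1)]. For T1 with ρ0 = 0.82 and ρ1 = 0.72, C = 10.111/6.143 = 1.646 and ln C = 0.498. Then √(119/4) = 5.454, and Φ(5.454 × 0.498 − 1.645) = Φ(1.073) = 0.858, as stated. The other four (0.935, 0.969, 0.873, 0.749) also reproduce. The sample size therefore rests on the ICC alone, and nothing below affects it.

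**Assumptions.** The documents give no native T1 or T2, dose or relaxivity, so all inputs here are assumed. The model is 1/T_post = 1/T_pre + ΔR, with ΔR proportional to tissue concentration. It follows that

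drop = T_pre − T_post = T_pre² × ΔR / (1 + T_pre × ΔR).

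**Same uptake, different native T1 (ΔR1 = 0.5 per second).**

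- Native 1000 ms: 1.0² × 0.5/1.5 = 0.333 s, a drop of 333 ms.
- Native 1400 ms: 1.4² × 0.5/1.7 = 0.576 s, a drop of 576 ms.
- Ratio 1.73. Over ΔR1 from 0.25 to 2.0 per second it runs from 1.81 to 1.55.

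**How spread in native T1 carries over.** The proportional sensitivity of the drop to T_pre is (2 + T_pre × ΔR)/(1 + T_pre × ΔR). At 1200 ms and 0.5 per second this is 2.6/1.6 = 1.625. The CV of the change is therefore about 1.6 times the CV of native T1. Simulation gives:

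| CV of native T1 | CV of T1 change, ΔR1 = 0.5/s | CV of T1 change, ΔR1 = 1.0/s | 90th/10th percentile ratio of change, ΔR1 = 0.5/s |
|---|---|---|---|
| 5% | 8% | 7% | 1.23 |
| 10% | 16% | 15% | 1.52 |
| 15% | 24% | 22% | about 1.9 |
| 20% | 32% | 29% | 2.35 |

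Uptake is identical in every row. On the rate scale each row would show a single value and no spread from native T1.

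**T2.** For native T2 of 45 to 75 ms and ΔR2 of 0.3 to 2.4 per second, equal uptake gives a change ratio of about 1.4 for 65 against 55 ms. The absolute changes are only about 0.6 to 11 ms, so the case rests on T1.

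**Dose and delay.** At native 1200 ms, halving the concentration (ΔR1 from 0.5 to 0.25 per second) moves the drop from 1.44 × 0.5/1.6 = 450 ms to 1.44 × 0.25/1.3 = 277 ms. The rate change itself halves. The rate scale thus removes dependence on native T1 but not on dose or delay.

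**Delay as planned.** The dynamic series in section 1.2 takes 3 × 100 s = 5 minutes after contrast. A high-resolution scan of unstated length follows, then two 3-minute MRF scans. The two post-contrast MRF scans are therefore at delays at least 3 minutes apart.

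**The case against.** The strongest reply is that the plan never presents the change as a measure of uptake. Section 7.3 only estimates it. The remark on native T1 in section 1.2 is background on converting a signal curve, whereas MRF measures T1 directly. Milliseconds are also the scale needed to compare with the published relaxation times that section 7.3 cites. All of this stands, and it is why the raw change should stay.

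Several stronger readings are tempting, but the documents do not support them:

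- *That the plan calls the change itself a baseline.* The full clause attaches the word to the parenchymal value at each phase. What remains is that estimating a change does not establish a value at each phase, and that baseline is a poor name for a post-contrast value.
- *That reduced doses will be common.* Section 3.2.4 excludes most patients with impaired kidney function, apart from those who are anuric and on dialysis.
- *That dose or delay distorts the left-right comparison.* Both breasts are imaged after one injection, so dose and delay are shared. Only native T1 matters there.
- *That delay is uncontrolled.* The scan order at one institution limits it, although no time in minutes is given.
- *That the distortion is two-fold or more.* Native T1 of 900 and 1500 ms at 0.5 per second gives drops of 279 and 643 ms, a 2.3-fold spread, but that range is chosen and not documented. At a native-T1 CV of 5%, the 90th-to-10th percentile ratio is only 1.23.

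It can also be said that rate changes can be computed from the same paired values at any time. That is true of the transform. It is less safe for dose and injection time, which no listed procedure collects.

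**Conclusion.** The point holds as a cheap improvement, not as a flaw that invalidates the endpoint. A component of the primary endpoint is planned only as a raw T1 and T2 change, and the post-contrast values lack the dose and delay needed to interpret them. Under the additive-rate assumption, variation in native T1 enters the T1 change multiplied by about 1.6 (at 1200 ms and 0.5 per second). A CV of 5% to 20% becomes about 8% to 32% with no difference in uptake. Where the trial falls in that range is unknown, because the documents give no native-T1 spread. The effect on T2 is small in absolute terms.

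The raw change remains a sound description of what happened in each woman. It is weak as a quantity to compare among women and, through native T1 alone, between sides. A reader might infer that changing scale would settle the matter. It would not, because dose and delay alter the uptake itself and have to be reported.

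**What to change.** In sections 7.3 and 2.2:

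1. Report pre-contrast and post-contrast T1 and T2 separately, in milliseconds.
2. Beside the raw change, report per location 1/T1_post − 1/T1_pre and the same for T2. Use this scale for any comparison of the pre-to-post change between women or sides.
3. Take agent, administered dose and injection-to-MRF time for each post-contrast scan from the clinical MRI record, and report the post-contrast values with them. Add these items to the abstraction in sections 4.2.4 and 4.3.
4. Keep the word baseline for pre-contrast values.
5. State that women who received no contrast contribute to the pre-contrast analysis only.

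The cost is a reciprocal transform of values already planned, a little more data abstraction, and a second scale that clinical readers know less well. Scanning, patient care and the ICC-based sample size of 30 are unchanged.
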